7.3.4. Analyses of tertiary objectives

The analysis on vaccine uptake is described in Section [7.2](#).

Completeness of seasonal influenza vaccination data in the EHR will be assessed by computing the percentage of subjects from the Cumulative vaccinated cohort Weeks 35-48 with data on influenza vaccines recorded in EHR, by Vaccine group:

- The denominator will be the number of subjects in the Cumulative vaccinated cohort Weeks 35-48
- The numerator will include all subjects from the denominator with the following respective data recorded in EHR:
 - Complete date of vaccination
 - Vaccine batch number
 - Both complete date of vaccination and vaccine batch number

Timeliness of vaccination data in the EHR will be assessed as follows:

- Time interval in days between the seasonal influenza vaccination dates and the dates at which the records were encoded in EHR will be summarized by Vaccine group using descriptive statistics (mean, standard deviation, median, range, first and third quartile) for the Cumulative vaccinated cohort Weeks 35-48. This time interval in days will also be graphically displayed.

Compliance in returning ADR cards is described in Section [7.3.1](#).

Timeliness of AEI reporting in EHR will be assessed as follows:

- Time interval in days between the first onset date of AEIs within the 7 days post-vaccination period and the dates at which the records were encoded in EHR will be summarized by Vaccine group and ADR cards returned status using descriptive statistics (mean, standard deviation, median, range, first and third quartile) for the Cumulative vaccinated cohort of Weeks 35-48. This time interval in days will also be graphically displayed.

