The weekly incidence rates (per 100 subjects) of AEIs within 7 days will be estimated as follows:

- The denominator will be the number of all subjects vaccinated the week before the week of interest (so reaching up to 7 days of follow-up post vaccination during the week of interest)
- The numerator will encompass all vaccinated subjects reporting the AEI within 7 days following vaccination with a seasonal influenza vaccine using data entered in the EHR (i.e., AEIs derived from ADR card and medically attended AEIs)

The cumulative incidence rates (per 100 subjects) of AEIs within 7 days will be estimated as follows:

- The denominator will be the number of all subjects vaccinated at any point from study start up to the week before the week of interest (i.e. cumulatively since the beginning of the study)
- The numerator will encompass all subjects from the denominator reporting the AEI within 7 days following vaccination with a seasonal influenza vaccine using data entered in the EHR (i.e., AEIs derived from ADR card and medically attended AEIs)

95% CI will be computed on the estimated incidence rates.

Analyses of the tertiary objectives

The percentage of subjects vaccinated with a seasonal influenza vaccine during the study vaccination period in the 10 participating GP practices will be tabulated by vaccine brand, age categories and CMO-specified risk groups.

Completeness of seasonal influenza vaccination data in the EHR will be assessed by computing the percentage of subjects with data on influenza vaccines recorded in EHR (date of vaccination, vaccine brand, vaccine batch number).

Timeliness of vaccination data in the EHR will be assessed as follows:

- Time interval in days between the seasonal influenza vaccination dates and the dates at which the records were entered in EHR will be summarized using descriptive statistics (mean, standard deviation, median, range, first and third quartile).

Timeliness of AEI reporting in EHR (medically attended AEs and from the card-based ADR reporting system) will be assessed as follows:

- Time interval in days between the first onset date of AEIs within the 7 days post-vaccination period and the dates at which the records were entered in EHR will be summarized using descriptive statistics (mean, standard deviation, median, range, first and third quartile).

The percentage of subjects who received and who returned the ADR card will be tabulated by vaccine brand.

Sensitive analyses

[figure not shown]

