5.3. Tertiary endpoints

- Seasonal influenza vaccination status among the subjects registered in the enrolled GP practices, overall, by vaccine brand, by age strata (6 months to 5 years; 6 to 12 years; 13 to 17 years; \geq 18-65 years; $>$ 65 years) and UK CMO-specified risk groups and date of vaccine administration collected in the EHR system
- Level of missing data related to vaccination information (date of event, vaccine brand, vaccine batch)
- Lag time between date of vaccine administration and date at which vaccination record is encoded in the EHR system
- Return of ADR cards
- Time interval between AEI onset date and recording in the EHR by source (medically attended vs via ADR cards)
- Time interval between the date data extraction and date at which the weekly report is generated

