6.4. Cumulative vaccinated cohorts

The Cumulative vaccinated cohorts (for each ISO Week 35 to 48, denoted as Weeks 35-35 to Weeks 35-48) will include all subjects from the Total eligible registered population

- who are vaccinated with a seasonal influenza vaccine at any point from study start up (i.e. 01SEP2017) up to the end of the week of interest (i.e. cumulatively since the beginning of the study)
- who are registered in EHR during the safety follow-up period (from vaccination up to 7 days post vaccination)

For example, the Cumulative vaccinated cohort Weeks 35-40 will include all subjects from the Total eligible registered population:

- who are vaccinated with a seasonal influenza vaccine at any point from study start up (i.e. 01SEP2017) up to the end of Week 40 (i.e. cumulatively since the beginning of the study)
- who are registered in EHR during the safety follow-up period (from vaccination up to 7 days post vaccination)

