12.2. Data derivation

12.2.1. Date derivation

The date of birth will be modified during the extract from EHR to protect personally identifiable information. The modified date of birth will contain the exact month and year of birth of the subjects, but the exact day of birth will not be provided and will be set to '01' for all the subject's birth dates.

If the vaccine administration date is incomplete or missing the following rule will be applied:

- Day missing: 15 is used (standard GSK imputation)
- Month or year is missing: vaccination not included in the statistical analysis

If the start date of the AEI is incomplete or missing, a conservative approach (worst case scenario) will be used for imputation for the vaccinated subjects. The rules for imputation are detailed below, the examples are given assuming 16OCT2017 as date of vaccine administration.

- Day missing:
 - Month of onset = month of administration: day of administration will be used (e.g. OCT2017 → 16OCT2017)
 - Month of onset > month of administration: first day of the month will be used (e.g. NOV2017 → 01NOV2017)
 - Month of onset < month of administration: AEI not included in the statistical analysis
- Month or year missing: AEI not included in the statistical analysis

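### SAP 7.3.4 measures vaccination-date completeness after records lacking month or year have been removed, so it picks up only missing days, and it states no numerator for brand

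*SAP*

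**What the plan says.** The protocol (section 5, analyses of the tertiary objectives) defines completeness as the percentage of subjects with three items recorded: "date of vaccination, vaccine brand, vaccine batch number". The tertiary endpoint, in Protocol section 4b and again in SAP 5.3, reads "Level of missing data related to vaccination information (date of event, vaccine brand, vaccine batch"), where I take the first item to be the vaccination date.

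SAP 7.3.4 sets up the analysis by Vaccine group. Its denominator rule is "The denominator will be the number of subjects in the Cumulative vaccinated cohort Weeks 35-48". It lists three numerators: complete date, batch number, and "Both complete date of vaccination and vaccine batch number". Brand is not among them.

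Entry to that cohort (SAP 6.4) is for subjects "who are vaccinated with a seasonal influenza vaccine at any point from study start up (i.e. 01SEP2017) up to the end of the week" in question, so the vaccination has to be placed in time. SAP 12.2.1 says how partial dates are handled:

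- "Month or year is missing: vaccination not included in the statistical analysis".
- "Day missing: 15 is used (standard GSK imputation").

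SAP 3.5 defines four Vaccine groups: Fluarix Tetra, Non-GSK, Unknown and All. SAP 7.1 tabulates exclusions from the cumulative cohorts with reasons, without listing the reasons. SAP section 10 declares only that cohorts and incidence rates were clarified.

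**The concern.** The table is meant to show how often vaccination records are incomplete, yet membership of its denominator depends on the item being measured. A record with no usable month or year, the worst form of incompleteness, is absent from both numerator and denominator. Those same records also drop out of the safety denominators, and this percentage would not show the loss.

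The gap for brand is different in kind. The primary and secondary rates are presented by brand, and the protocol requires adverse events to be linked to a specific brand and batch. Readers therefore need to know how often brand is missing. The SAP's own endpoint promises that information, and its analysis section gives no numerator for it.

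Protocol section 4b presents the evaluation of data completeness as an EU requirement, so the table serves a stated purpose of the study.

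**Working it through.** **No figure to reproduce.** Neither document states an expected rate of missing dates, brands or batches. The check is algebra on the SAP rules, with assumed rates shown as a range.

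**Inputs**

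- N = number of vaccination records. SAP 3.1 expects 5,000 vaccinated subjects; this is used only for scale.
- m = share of records with month or year missing. These are excluded (SAP 12.2.1). Assumed 0 to 10%.
- d = share with only the day missing. These are kept, with day 15 imputed. Assumed 0 to 10%.

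**Step 1: are day-missing records retained?** The imputed dates are 15 September, 15 October and 15 November 2017. In SAP Annex 4 they fall in weeks 37, 41 and 46, all inside the window. Subject to the other cohort criteria, these records stay in the denominator. They have no complete recorded date, so they should fail that numerator.

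**Step 2: formulas**

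- Denominator under the SAP: N(1-m). Records with a complete date: N(1-m-d).
- SAP date completeness: (1-m-d)/(1-m).
- Completeness over all records: 1-m-d.
- Overstatement: the difference, which is m(1-m-d)/(1-m).

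**Step 3: numbers**

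| m | d | SAP rule | All records | Overstatement (points) |
|---|---|---|---|---|
| 0% | 10% | 90.0% | 90.0% | 0.0 |
| 2% | 0% | 100.0% | 98.0% | 2.0 |
| 5% | 0% | 100.0% | 95.0% | 5.0 |
| 5% | 5% | 94.7% | 90.0% | 4.7 |
| 10% | 0% | 100.0% | 90.0% | 10.0 |
| 10% | 10% | 88.9% | 80.0% | 8.9 |

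One row in full, m=10% and d=10%: the denominator is 5,000 × 0.90 = 4,500 and the complete dates number 5,000 × 0.80 = 4,000. The SAP gives 4,000/4,500 = 88.9%; over all records it is 4,000/5,000 = 80.0%.

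With d=0 the SAP figure is 100% whatever m is. With m=0 the two measures agree. The numerator for date and batch together is inflated by the same factor, 1/(1-m), because an undatable record can never count in it.

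**Step 4: brand.** The protocol names date, brand and batch; SAP 5.3 names the same three; SAP 7.3.4 has date, batch, and both. If the Unknown group means that brand was not recorded, which the SAP does not say, brand completeness among datable records is 1 - N(Unknown)/N(All). Unknown shares of 1%, 5%, 10% and 20% would give 99%, 95%, 90% and 80%.

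**The case against.** Four points can be made for the plan.

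1. A reader might infer that date completeness comes out near 100% by construction. It does not. Day-missing records are retained and count as incomplete, so the result falls with d: at m=0 and d=10% it is 90%. It would be close to 100% only if day-level missingness were rare, and the documents give no rate. This stands.
2. A reader might also infer that brand completeness cannot be obtained at all. That too is more than the documents support. Uptake (7.2) and completeness (7.3.4) are both shown by Vaccine group, so the Unknown and All counts carry much of the information. A brand percentage within the Fluarix Tetra or Unknown column would say little, because brand largely defines the column. This stands in part: the SAP neither defines Unknown nor assigns it to the endpoint.
3. The section 7.1 exclusion table is a natural place for records dropped for missing month or year. This is a partial answer, since that reason is not named and no completeness percentage follows from it. The table shells are in a separate annex that is not available here, so a row for date exclusions or for brand cannot be ruled out.
4. Nothing suggests that m is large. The protocol's introduction says the EHR gave a reliable vaccination denominator in the earlier pilots. This stands as a reason not to lean on any one value of m. It does not alter the direction of the bias.

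**Conclusion.** The point holds in two parts. First, date completeness under SAP 7.3.4 reflects day-level missingness only and is too high whenever any record lacks month or year. The size is m(1-m-d)/(1-m): 2, 5 or 10 points at m=2%, 5% or 10% with d=0, and slightly less when d is above zero. These sizes rest on assumed rates; the direction follows from the SAP rules alone. Second, brand has no stated numerator although the protocol analysis and the endpoint in both documents call for it, and section 10 does not declare the change.

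As written, the table does not fully deliver a stated objective. The consequence is limited: the objective is tertiary and descriptive, and no incidence rate, confidence interval or sample size depends on this table.

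**What to change.** - **Denominator.** For the completeness table only, use all subjects in the Total eligible registered population with a seasonal influenza vaccination record attributable to the study season, including those with month or year missing.
- **Attribution rule.** State how undatable records are assigned to the season, since a record without month or year cannot be placed by its own date. The date of entry in the EHR is one option; the timeliness analysis in 7.3.4 already uses it. Without a rule, vaccinations from outside the study period could be counted as study incompleteness.
- **Brand.** Add numerators for brand and for date, brand and batch together, read mainly in the Vaccinated (All) column. Alternatively, define the Unknown group and state that N(Unknown)/N(All) is the brand-missing measure. No extra overall presentation is needed, because All is already a Vaccine group.
- **Exclusions.** In the section 7.1 table, name missing month or year of vaccination as a reason and give the count.
- **Declaration.** If brand is left out on purpose, say so in section 10.

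The cost is a few lines of SAP text and a wider query for one table. The cohorts used for the safety analyses stay as they are.

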The present collaborative pilot study between MAH GlaxoSmithKline Biologicals (GSK) and the Clinical Informatics and Health Outcomes Research Group at the University of Surrey builds on the lessons learned from the pilot studies (EPI-FLU-045 VS UK and EPI-FLU-046 VS UK). The study addresses the EMA commitment for enhanced safety surveillance of seasonal vaccines in Europe. The EPI-FLU-045 VS UK pilot study showed that the proposed surveillance setting in the UK was suitable for rapid detection and evaluation of AEIs during an influenza season. Nevertheless, the outcomes were not available in a near real time manner. This was successfully addressed in the EPI-FLU-046 VS UK pilot study.

Both pilot studies confirmed that a card-based ADR reporting system in addition to report of AEI from routinely collected was a valid methodology. In the EPI-FLU-046 VS UK pilot study, the ADR cards were customized (including pre-specified EMA AEIs) and a specific field was created to allow

reporting that no AEI was experienced during the period of interest. Thanks to those modifications, the return rate drastically increased up to approximately 50%. In addition, the encoding of AEIs was facilitated for GPs which led to a more standardised and more accurate way to ultimately collect the AEIs.

The EHR data provided a reliable estimate of the denominator of vaccines administered throughout the participating GP practices. The use of routinely collected data provided additionally demographic characteristics and account for underlying conditions, or comorbidities, discharged letter from hospital or prescriptions from pharmacist for patients registered in the participating GP practices.

The primary purpose of the 2016/17 pilot study was to improve the combination of a card-based ADR reporting system and the use of routine data to collect adverse events following vaccination with seasonal influenza vaccines, as per EMA guidance and PRAC requirements. The ADR cards had been further customized since the first pilot study to account for the EU requirements. The 2017/18 pilot study will build on the lessons learned from the first 2 pilot studies and aim to continue standardizing the approach to collect and report AEIs.

The results of the current study will further inform decisions regarding future influenza vaccine safety surveillance and contribute to the cumulative awareness and knowledge associated with reporting of adverse event following immunisation (AEFI) in Europe.

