1. General Practice EHR data recorded by the practice team. Weekly data about vaccine exposure, and any subsequent AEIs will be uploaded (anonymised) to University of Surrey. The EHR data contains both AEIs recorded by the practice team, as well as data reported to the GP practice on an ADR card by a vaccinated patient.
2. ADR cards completed by patients. Among the 10 participating GP practices, patients who are vaccinated against influenza will be provided ADR cards. These ADR cards customised following practice feedback to match EMA requirements will be used to collect AEIs reported after the receipt of influenza vaccination.

The method and governance procedure has been developed by the University of Surrey, using an approved provider, Apollo. If not applicable, alternatively, another approved data extraction supplier will be chosen, or the relevant study data will be directly extracted by the University of Surrey team using standard data extraction tools such as Morbidity Information Query Export Syntax (MIQUEST), tool sponsored by the Department of Health.

Data extractions will be conducted in accordance with the Research Group's standard operating procedures in data extraction, pseudonymisation, and transfer.

Pseudonymisation is a process that involves the removal of all personal identifiers – such as name, date of birth, etc. Furthermore, encrypted data will be kept during transfer and on a secure network that meets NHS Information Governance standards to minimise the risk of re-identification. Pseudonymisation is the standard approach for this type of surveillance. A legally binding definition of pseudonymisation has been introduced into European law^x on the recommendation of the European Data Protection Supervisor (EDPS)^{xi}.

Data are anonymised (strictly defined as “pseudonymised”) as near to source as possible. All data are strongly encrypted by a combination of symmetric and asymmetric encryption algorithms: Triple DES¹ and RSA 1024² before transmission, and utilises public and private key pairs unique to each project. Pseudonymisation is applied at this stage to allow for backwards identification should there be a need to do so as part of an ethically approved study.

For this study, it is required to link an adverse event to the vaccine (specific brand and batch number) administered. Pseudonymisation allows this without knowing any of the strong personal identifiers of that individual.

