3.3.2. Adverse Drug Reaction card

In order to facilitate the coding of data using a standardised approach, the 10 enrolled GP practices will also distribute an ADR card to their subjects receiving seasonal influenza vaccine or, as appropriate, to their parent or carer.

Subjects will be instructed to record adverse events (refer to [Annex 3](#)) within 7 days following vaccination and to return the card to their GP practice not later than 14 days post-vaccination. Data recorded on these cards will then be recorded by the GP staff into the subject's EHR. The coding will follow a standardised approach to data recording (refer to [Annex 2](#)) and will include a specific code to indicate that the information is derived from those cards.

Of note, the intent will be to issue cards to all vaccinated patients belonging to the enrolled GP practices, however, considering the UK influenza vaccination plan, some vaccinations are expected to occur outside of the GP settings. These are described as opportunistic vaccination, performed by third parties including pharmacists and thus it cannot be excluded that for some patients, ADR cards will not be distributed. These vaccinations will still be encoded in the EHR and those subjects will be included in the study. The adverse events (AEs) will be captured through the routine data collection process (refer to Section 3.3.1).

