4.3. Tertiary objectives

- To estimate on a weekly basis the vaccine uptake among the subjects registered in the enrolled GP practices, by age strata (6 months to 5 years; 6 to 12 years; 13 to 17 years; \geq 18-65 years; $>$ 65 years) and UK CMO-specified risk groups
- To assess the completeness of vaccination data in the EHR
- To assess the timeliness of availability of vaccination data in the EHR
- To evaluate the return rate of ADR cards
- To assess the timeliness of AEI reports in the EHR from medically attended AEIs and from the card-based ADR reporting system
- To assess the timeliness of generating weekly reports

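### AEI reporting timeliness is defined by source of the record but analysed by whether the subject returned a card, so the by-source endpoint is not delivered

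*SAP*

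**What the plan says.** The SAP states the objective in section 4.3: "To assess the timeliness of AEI reports in the EHR from medically attended AEIs and from the card-based ADR reporting system". The matching endpoint in section 5.3 is "Time interval between AEI onset date and recording in the EHR by source (medically attended vs via ADR cards"), and protocol section 4b defines it in the same way. The protocol's description of the tertiary analyses (section 5) also names both sources: "Timeliness of AEI reporting in EHR (medically attended AEs and from the card-based ADR reporting system) will be assessed as follows". The text that follows there gives the interval and the summary statistics, with no explicit split.

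SAP section 7.3.4 supplies a split, but a different one. The interval "will be summarized by Vaccine group and ADR cards returned status using descriptive statistics", in the whole cumulative cohort for weeks 35 to 48. The returned group is not limited to card-derived records. SAP section 10 mentions clarified cohorts and incidence rates and says nothing about timeliness.

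Two further statements bear on the point. Protocol section 5, under data extraction, says: "The EHR data contains both AEIs recorded by the practice team, as well as data reported to the GP practice on an ADR card". SAP section 3.3.2 says that the coding of card data "will include a specific code to indicate that the information is derived from those cards".

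**The concern.** A subject who returns a card may also have consulted the practice within 7 days of vaccination. That subject's record can then hold AEIs from both routes. A split on card return sends all of them to the same row, whatever their source.

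The two routes have different delays. A medically attended AEI can be coded when the patient is seen. A card AEI waits for the card to come back and for staff to enter it; subjects are asked "to return the card to their GP practice not later than 14 days post-vaccination". The protocol presents the cards as its enhancement over routine data and near real-time analysis as a design aim. It also reports that outcomes were not available in near real time in the first pilot. Separate lags for the two routes would show what the cards cost in time. They would also show whether the three-week wait before each weekly report (SAP section 9.1.1) suits both routes. The planned table does not provide that separation.

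**Working it through.** **Step 1. What each row contains.** The documents give no figure to reproduce, so the first check is a classification under the rule in SAP section 7.3.4.

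| Card returned? | Source of AEI record | Row under SAP 7.3.4 | Row under SAP 5.3 |
|---|---|---|---|
| Yes | Card | Returned | Card |
| Yes | Medically attended | Returned | Medically attended |
| No | Medically attended | Not returned | Medically attended |

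The second line is where the splits part. The returned row contains both sources. The not-returned row contains one source but lacks the returners' part of it. The two splits coincide only if no returner has a medically attended AEI.

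**Step 2. Effect on the returned row.** Let s be the share of records in that row that come from consultations, and let L_card and L_cons be the mean lags. Then

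returned-row mean = (1 - s) × L_card + s × L_cons = L_card - s × (L_card - L_cons).

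The documents give none of these three quantities. Assume for illustration L_cons = 1 day and L_card = 10 days, so the mean is 10 - 9s:

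| s (assumed) | Returned-row mean (days) | Below card-only mean by (days) |
|---|---|---|
| 0% | 10 | 0 |
| 5% | 10 - 0.45 = 9.55 | 0.45 |
| 10% | 10 - 0.9 = 9.1 | 0.9 |
| 20% | 10 - 1.8 = 8.2 | 1.8 |
| 40% | 10 - 3.6 = 6.4 | 3.6 |

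**Step 3. Why the return rate does not give s.** The protocol reports that in the second pilot "the return rate drastically increased up to approximately 50"%. If consulting were unrelated to returning, that would put a share p of about 0.5 of all medically attended AEIs in the returned row. This is a different fraction from s. With M medically attended AEIs and C card AEIs in total,

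s = pM / (pM + C), so C/M = p(1 - s)/s.

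With p = 0.5, s = 5% corresponds to C/M = 0.5 × 0.95/0.05 = 9.5; s = 10% to 4.5; s = 20% to 2; and s = 40% to 0.75. One return rate is compatible with the whole range in Step 2, and the documents do not give C/M.

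**Step 4. What the 14 days bound.** The return limit runs from vaccination; the analysed interval runs from AEI onset. For onset on day d, a card returned on time adds at most 14 - d days before data entry: 14 days for onset on day 0 and 7 days for onset on day 7.

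**Step 5. Feasibility of the by-source split.** Card entries carry their own code (SAP section 3.3.2), and the primary analysis (SAP section 7.3.2) already has to pick out AEIs reported on the card. Record source must therefore be derived in any case.

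**The case against.** The strongest reply is that card-returned status was meant as a proxy for source and may serve well enough. If few returners consult, s is small and the returned row is close to the card lag. If recording lag at consultation is also unrelated to card return, the not-returned row estimates consultation lag without bias. The table layouts are in a separate document that is not available here and may show a by-source table. The endpoint is tertiary, all analyses are descriptive, and no stated decision rule uses this table. All of this stands, and it limits the importance of the point. It does not make the SAP text match its own endpoint, and the documents do not show that s is small.

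Some stronger readings are tempting and should be set aside:

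- **That both rows are mixed.** Only the returned row is. The other is incomplete but comes from a single source.
- **That about half of the returned row is consultation records, from the 50% return rate.** Step 3 shows that this is the wrong fraction. Some vaccinees may also receive no card yet stay in the cohort as non-returners. If the 50% is per card issued, the returned share of the cohort is lower still.
- **That card lag is up to 14 days plus entry time whatever the onset day.** Step 4 shows that the bound shrinks as onset gets later.
- **That the mixture would be hidden in one number.** SAP section 7.3.4 asks for measures of centre, spread and quartiles and for a graph. A mixture of short and long lags might be visible there, though it would not be labelled by source.

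**Conclusion.** The mismatch is real and is wrong as written. A subject-level split stands in for an endpoint defined on records, the SAP lists no such change, and following section 7.3.4 literally produces no result by source. The returned row would tend to understate card lag if consultation records are faster, which is an assumption. The understatement equals s times the difference in mean lags: about 0.5 to 3.6 days for s between 5% and 40% under the assumed lags of 1 and 10 days, and nothing if s is zero. The true size cannot be obtained from the documents.

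A reader might infer that the safety results are compromised. They are not. The primary and secondary incidence rates do not use this split. This is a minor point of consistency, limited to what the SAP text says.

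**What to change.** In the AEI timeliness paragraph of SAP section 7.3.4, replace card-returned status as the stratifier with source of the AEI record (card-coded or medically attended), identified by the card code described in SAP section 3.3.2. Add one sentence stating that an AEI recorded by both routes contributes one interval to each source. That sentence is needed because the section measures from first onset without saying whether the unit is the subject or the event, or which recording date applies when there are two. Card-returned status may be kept as an additional split.

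The cost is a changed phrase, one added sentence and a check that the matching table layout agrees. No new data are needed, since record source is already required for the primary analysis.
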